APPENDIX D. ACTIVITY SCHEDULE

The following table shows the required activities for this study. The individual activities are described in detail in [Appendix E](#).

Study Activities

Activity	Screening		Cycle 1				Cycles 2 to 3				Cycles 4+		Response Confirmation ⁸	End-of-Treatment	Safety Follow-Up ^b	
	Day -1	Day -21 to Day -1	Day 1	Day 8	Day 15	Day 22	Day 1	Day 8	Day 15	Day 22	Day 1	Days 8, 15, 22				
INTERVIEWS & QUESTIONNAIRES																
Informed consent	✓															
Confirm eligibility	✓		✓													
Medical/oncology/surgical history	✓		✓													
History of/subsequent myeloma therapy	✓		✓													
Adverse event assessment	✓		✓	✓	✓	✓	✓	✓	✓	✓	✓	✓	✓	✓	✓	✓
Prior/concomitant therapy	✓		✓	✓	✓	✓	✓	✓	✓	✓	✓	✓	✓	✓	✓	✓
ECOG performance status	✓		✓													
Clinic visit	✓		✓	✓	✓	✓	✓	✓	✓	✓	✓	✓	✓	✓	✓	✓
IMWG response assessment	✓		✓	✓	✓	✓	✓	✓	✓	✓	✓	✓	✓	✓	✓	✓
LOCAL LABORATORY TESTS & EXAMINATIONS																
Complete physical examination	✓															
Symptom-directed physical examination			✓	✓	✓	✓	✓	✓	✓	✓	✓	✓	✓	✓	✓	✓
Height (screening only) and weight	✓		✓	✓	✓	✓	✓	✓	✓	✓	✓	✓	✓	✓	✓	✓
Vital signs	✓		✓	✓	✓	✓	✓	✓	✓	✓	✓	✓	✓	✓	✓	✓
12-Lead electrocardiogram	✓		✓	✓	✓	✓	✓	✓	✓	✓	✓	✓	✓	✓	✓	✓

Activity	Screening				Cycle 1				Cycles 2 to 3				Cycles 4+		Response ^a	End-of-Treatment	Safety Follow-Up ^b	
	Day -21 to Day -1	Day 1	Day 8	Day 15	Day 22	Day 1	Day 8	Day 15	Day 22	Day 1	Day 8	Day 15	Day 22	Day 1	Days 8, 15, 22			
Hematology	✓	✓	✓	✓	✓	✓	✓	✓	✓	✓	✓	✓	✓	✓		✓	✓	✓
Clinical chemistry	✓	✓	✓	✓	✓	✓	✓	✓	✓	✓	✓	✓	✓	✓		✓	✓	✓
TLS panel ^c		✓																
Serum pregnancy test	✓	✓	✓	✓	✓	✓	✓	✓	✓	✓	✓	✓	✓	✓	✓	✓	✓	✓
Urine pregnancy test ^d		✓	✓	✓	✓	✓	✓	✓	✓	✓	✓	✓	✓	✓	✓	✓	✓	✓
Coagulation panel	✓	✓																
Amylase, lipase	✓																	
Skeletal survey	✓	✓ ^e												✓ ^e		✓ ^e	✓ ^e	✓ ^e
Plasmacytoma evaluation	✓	✓ ^f												✓ ^f		✓ ^f	✓ ^f	✓ ^f
CENTRAL LABORATORY TESTS																		
Serum β2 microglobulin	✓																	
Viral serologies	✓																	
Serum protein immunofixation	✓	✓												✓		✓	✓	✓
Serum protein electrophoresis	✓	✓												✓		✓	✓	✓
Serum quantitative immunoglobulins	✓	✓												✓		✓	✓	✓

Activity	Screening				Cycle 1				Cycles 2 to 3				Cycles 4+		Response Confirmation ^a	End-of-Treatment	Safety Follow-Up ^b		
	Day -21 to Day -1	Day 1	Day 8	Day 15	Day 22	Day 1	Day 8	Day 15	Day 22	Day 1	Day 8	Day 15	Day 22	Day 1				Days 8, 15, 22	
Serum free light chain	✓	✓ ^g												✓ ^g	CR/sCR	✓ ^g		30-Day	
Urine protein immunofixation	✓	✓												✓	h	h			
Urine protein electrophoresis	✓	✓												✓	h	h			
Bone marrow aspirate (including MRD) ⁱ	✓													✓	CR/sCR	opt			
Bone marrow core biopsy	✓													✓	CR/sCR	opt			
Venetoclax pharmacokinetic sample		✓		✓										✓	Cycles 4, 6, 8 only				
Pomalidomide pharmacokinetic sample		✓		✓															
Biomarker research blood sample		✓												✓	Cycles 4, 5, 9 only				
Optional biomarker research blood sample (expansion phase only)		✓												✓	Cycle 3 only				
Rx TREATMENT																			
Venetoclax																			Days 1 through 28 of each cycle
Pomalidomide																			Days 1 through 21 of each cycle

Activity	Screening				Cycle 1				Cycles 2 to 3				Cycles 4+		Response ^a	End-of-Treatment	Safety Follow-Up ^b		
	Day -21 to Day -1	Day 1	Day 8	Day 15	Day 22	Day 1	Day 8	Day 15	Day 22	Day 1	Day 8	Day 15	Day 22	Day 1	Days 8, 15, 22				
Dexamethasone		✓	✓	✓	✓	✓	✓	✓	✓	✓	✓	✓	✓	✓	✓				
Subject diary		✓	✓	✓	✓	✓	✓	✓	✓	✓	✓	✓	✓	✓	✓		✓		
Pomalidomide education and counseling guidance document and pomalidomide information sheet ¹		✓				✓				✓				✓					

CR = complete response; ECOG = Eastern Cooperative Oncology Group; IMWG = International Myeloma Working Group; MRD = minimal residual disease; PFS = progression-free survival; sCR = stringent complete response; TLS = tumor lysis syndrome; VGPR = very good partial response

- Required for every response of \geq VGPR AND if subject is to be discontinued for progressive disease (i.e., progressive disease must be confirmed).
- The safety follow-up visit will occur approximately 30 days after the last dose of study drug or before start of subsequent treatment, whichever occurs first.
- For subjects with t(11;14) and $>$ 50% bone marrow plasma cell infiltration or creatinine clearance $<$ 50 mL/minute, TLS laboratory samples should be collected at approximately 6 hours after the first dose with venetoclax.
- Females of childbearing potential with regular or no menstrual cycles must have pregnancy tests weekly for first month and then monthly. Females of childbearing potential with irregular menstrual cycles must have pregnancy tests weekly for the first month and then every 14 days while taking pomalidomide, at end-of-treatment, and 14 and 28 days following the last dose of pomalidomide.
- if clinically indicated.
- Performed during treatment only to confirm a minimal response or better, or to confirm progressive disease, or as clinically indicated.
- Collect only for subjects without measurable M-protein in screening serum or urine.
- Urine protein electrophoresis and urine immunofixation collection is mandatory for confirmation of VGPR, CR, and sCR, regardless of whether urine M-protein was measurable at baseline.
- An MRD assessment will be required for every response of \geq VGPR AND if subject is to be discontinued for progressive disease AND 6 and 12 months post-confirmation of CR/sCR for subjects who have maintained this response.

- j. Pomalidomide education and counseling guidance document for each gender as well as pomalidomide information sheet must be completed and signed before starting pomalidomide and each time the subject receives a new supply of pomalidomide.

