The BELLINI study (Study M14-031), a global, Phase 3, multicenter, randomized, double-blind study of bortezomib and dexamethasone in combination with either venetoclax or placebo in subjects with R/R MM who are sensitive or naïve to proteasome inhibitors, was unblinded as per protocol for the final analysis of the primary efficacy endpoint. As of the data cutoff date of 26 November 2018, 194 subjects were randomized to the venetoclax arm and 97 subjects to the placebo arm (2:1 randomization). The BELLINI study met its primary endpoint of progression-free survival (PFS; 22.4 versus 11.5 months, hazard ratio [HR] 0.63, 95% confidence interval [CI]: 0.44 - 0.90) and showed statistically significant improvements in overall response rate (ORR; 82% versus 68%) and very good partial response (VGPR) or better (59% versus 36%) in the venetoclax arm compared to the control arm. However, there were 51 deaths in the safety analysis set, 40 (20.7%) in the venetoclax arm and 11 (11.5%) in the placebo arm (the median overall survival [OS] has not been reached in either arm). The imbalance was predominantly seen in the treatment-emergent deaths which are those occurring on-therapy or within 30 days after the last dose of therapy. Among the 14 treatment-emergent deaths reported, 13 (6.7%) were in the venetoclax arm and 1 (1.0 %) in placebo arm. Of the 13 treatment-emergent deaths in the venetoclax arm, 8 were attributed by investigator to an event of infection; more than half of the deaths were also in the setting of refractory or progressive disease (PD). Although the majority of infection-related deaths occurred within 180 days of starting study treatment, some have occurred later, even after a year or more on treatment. A higher rate of Grade 3 or 4 neutropenia was seen in the venetoclax arm compared to placebo but an association of infection-related deaths with neutropenia has not been established at this point. Among the 37 nontreatment-emergent deaths (those occurring more than 30 days after the last dose of study treatment), 27 (14.0%) were in the venetoclax arm (6 deaths attributed to infection, 3.1%), and 10 (10.4%) in the placebo arm (2 deaths attributed to infection, 2.1%). After the data cutoff of 26 November 2018, additional deaths were reported in the BELLINI trial. As of 01 March 2019, there were 65 deaths in the safety analysis set, 48 (24.7%) in venetoclax arm and 17 (17.5%) in the placebo arm.

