5.6 Follow-Up for Subject Withdrawal from Study

To minimize missing data for efficacy and safety assessments, subjects who prematurely discontinue study drug treatment should continue to be followed for all regularly scheduled visits, unless subjects have decided to discontinue the study participation entirely (withdrawal of informed consent). Subjects should be advised on the continued scientific importance of their data even if they discontinue treatment early.

If a subject discontinues study participation (withdrawal of informed consent), the procedures outlined for the end-of-treatment visit should be completed as soon as possible, preferably within 2 weeks. In addition, if subject is willing, a 30-day follow-up phone call after the last dose of study drug may be completed to ensure all treatment-emergent AEs/SAEs have been resolved to a \leq Grade 1 or baseline level or, in the opinion of the investigator, the event is unlikely to resolve.

All attempts must be made to determine the date of the last study drug dose and the primary reason for the discontinuation of the study drugs or study participation. The information will be recorded on the appropriate eCRF page. However, these procedures should not interfere with the initiation of any new treatments or therapeutic modalities that the investigator feels are necessary to treat the subject's condition. Following the discontinuation of the study drugs, the subject will be treated in accordance with the investigator's clinical judgment, irrespective of whether or not the subject decides to continue participation in the study.

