Important Medical Event Requiring Medical or Surgical Intervention to Prevent Serious Outcome	An important medical event that may not be immediately life-threatening or result in death or hospitalization but, based on medical judgment, may jeopardize the subject and may require medical or surgical intervention to prevent any of the outcomes listed above (i.e., death of subject, life threatening, hospitalization, prolongation of hospitalization, congenital anomaly, or persistent or significant disability/incapacity). Additionally, any elective or spontaneous abortion or stillbirth is considered an important medical event. Examples of such events include allergic bronchospasm requiring intensive treatment in an emergency room or at home, blood dyscrasias or convulsions that do not result in inpatient hospitalization, or the development of drug dependency or drug abuse.

Hospitalization of a subject to allow observation and management (e.g., intravenous [IV] hydration) for the purpose of TLS prophylaxis will not be captured as an SAE unless there is an additional reason for hospitalization or an additional criterion for seriousness other than hospitalization (e.g., abnormal postdose TLS laboratories that necessitate therapeutic medical intervention, etc.).

All AEs reported from the time the study drugs are administered until 30 days after discontinuation of any study drug will be collected whether solicited or spontaneously reported by the subject. In addition, protocol-related SAEs and nonserious AEs will be collected from the time the subject signed the study-specific informed consent.

All AEs should be followed until resolution, return to baseline, or determined to be stable per the investigator.

AE = adverse event; SAE = serious adverse event

* Only if considered by the investigator to be causally related to study-required procedures.

a. 30 Days after the last dose of venetoclax.

Adverse Event Severity and Relationship to the Study Drugs

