AEs will be monitored throughout the study to identify any of special interest that may indicate a trend or risk to subjects. The following AEs of special interest (serious and nonserious) are to be entered into the electronic data capture system immediately (i.e., no more than 24 hours after the site becoming aware of the event):

- TLS

Dose-Limiting Toxicity

DLTs (as defined Section 6.5) will be assessed during the first cycle of venetoclax and pomalidomide dosing. Toxicities occurring after the first cycle of dosing will also be evaluated by the investigator and the AbbVie TA MD and taken into consideration for dose-escalation decisions.

Pregnancy

While not an AE, pregnancy in a study subject must be reported to AbbVie within 1 working day of the site becoming aware of the pregnancy. If a pregnancy occurs in a study subject or in the partner of a study subject, information regarding the pregnancy and the outcome will be collected. In the event of pregnancy occurring in a subject's partner during the study, written informed consent from the partner must be obtained before collection of any such information. A separate consent will be provided by AbbVie for this purpose. Pregnancies in study subject's partners will be collected from the date of the first dose through 30 days following the last dose of study drug.

The pregnancy outcome of an elective or spontaneous abortion, stillbirth, or congenital anomaly is considered an SAE and must be reported to AbbVie within 24 hours of the site becoming aware of the event.

Deaths

Deaths that occur during the protocol-specified AE reporting period that are attributed by the investigator solely to progression of MM should be recorded only on the study completion eCRF with

disease progression as the reason for discontinuation and not on the AE eCRF. All other on-study deaths, regardless of relationship to study drug, must be recorded on the AE eCRF and immediately reported to the sponsor.

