APPENDIX M. PROTOCOL AMENDMENT SUMMARY OF CHANGES

Previous Protocol Versions

Protocol	Date
Version 1.0	02 February 2018
Version 2.0	11 June 2018
Version 3.0	15 March 2019
Version 4.0	02 October 2019

The purpose of this amendment is to correct minor clerical errors for consistency and other administrative changes throughout the protocol in addition to the following:

- Rationale:** To update pneumococcal and influenza vaccination requirements in Section 5.4.
 - Updated pneumococcal influenza vaccination requirements to remove requirement for re-vaccination if subjects were already vaccinated.
- Rationale:** To update the list of signatories in Appendix C per current standard operating procedure.
 - Replaced [REDACTED] and [REDACTED] with [REDACTED].
 - Removed [REDACTED] as a signatory.
- Rationale:** To delete the progression-free survival follow-up visits.
 - Removed progression-free survival follow-up visits to the Schedule of Activities, Appendix D.
 - Removed the subject criteria for progression-free survival follow-up and the frequency of the visits in Appendix E.
- Rationale:** To delete the survival follow-up assessments.
 - Removed survival follow-up visits to the Schedule of Activities, Appendix D.
 - Removed the survival status activity row to the Schedule of Activities, Appendix D.
 - Removed the summary of the data collected and the frequency for the survival follow-up visits in Appendix E.

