## **7.0 Safety Analyses**

### **7.1 Analysis of Adverse Events**

AE analysis will only include treatment-emergent events (those that have an onset on or after the day of the first dose of any study drug), and will not include AEs that have an onset of more than 30 days after the last dose of any study drug.

Treatment-emergent AEs will be coded and summarized by system organ class and preferred term according to the Medical Dictionary for Regulatory Activities (MedDRA) AE coding dictionary. The percentage of subjects experiencing an AE at a given severity will be provided along with the NCI CTCAE version 4.03 toxicity grade and relationship to the study drugs. Serious AEs, AEs leading to discontinuation of treatment, and AEs leading to death will be summarized. All summaries will be done by dose. For the study as a whole, AEs will be evaluated and summarized.

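### Subjects who start new therapy before day 30 have no guaranteed contact for the rest of the 30-day adverse event window, and Section 5.6 asks for off-treatment visits that Appendix D does not schedule

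*Protocol*

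**What the plan says.** - **Timing of the last visit.** Protocol Appendix D, footnote b: "The safety follow-up visit will occur approximately 30 days after the last dose of study drug or before start of subsequent treatment, whichever occurs first".
- **Collection window.** Protocol Section 6.1 takes adverse events from the start of dosing "until 30 days after discontinuation of any study drug will be collected whether solicited or spontaneously reported by the subject".
- **Analysis window.** SAP Section 7.1 counts events from the first dose onward and "will not include AEs that have an onset of more than 30 days after the last dose of any study drug". Neither document shortens the window when another treatment starts.
- **Deaths and serious events.** Under Section 6.1, deaths that the investigator attributes only to myeloma progression go on the study completion form. For the rest: "All other on-study deaths, regardless of relationship to study drug, must be recorded on the AE eCRF and immediately reported to the sponsor". Section 6.3 requires serious events to be reported within 24 hours of the site learning of them.
- **After drug is stopped.** Section 5.6 says that subjects who stop drug early "should continue to be followed for all regularly scheduled visits", unless they withdraw consent. It mentions a 30-day phone call, but only as an option and only in the paragraph on consent withdrawal.
- **The schedule.** The last two columns of Appendix D are End-of-Treatment and the 30-day safety follow-up. Appendix M confirms that the absence of later visits is deliberate: "Removed progression-free survival follow-up visits to the Schedule of Activities, Appendix D" and "Removed survival follow-up visits to the Schedule of Activities, Appendix D".
- **Progression-free survival (PFS).** SAP Section 4.3.2 counts progression as an event even when it occurs after study drug was discontinued, and counts death from any cause.

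**The concern.** Safety is the primary objective and Section 4.2 states that there is no control group. An event that goes unrecorded lowers the reported rate directly, and no comparator shares the loss.

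The loss would not be random. Section 5.5 requires withdrawal on confirmed progression, and progressing subjects are the ones likely to start another therapy within 30 days. The protocol itself treats this as a period of infection risk: Sections 5.4 and 6.4 call for anti-infective prophylaxis for at least 30 days upon progression. Section 2.1 reports that, in the phase 3 venetoclax trial, 8 of 13 treatment-emergent deaths on venetoclax were attributed to infection and more than half of the 13 occurred with refractory or progressive disease.

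The conflict between Section 5.6 and Appendix D is a separate source of uneven data. One site can keep seeing a subject who stopped drug without progressing and another can stop, and each can point to the protocol. That affects off-treatment safety data and PFS.

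**Working it through.** **1. The windows side by side**

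| Item | Ends at | Shortened by new therapy? |
|---|---|---|
| Adverse event collection (Protocol 6.1) | 30 days after drug stops | No |
| Adverse event analysis (SAP 7.1) | 30 days after last dose | No |
| Safety follow-up visit (Appendix D, footnote b) | About day 30, or before new therapy | Yes |
| Phone call (Protocol 5.6) | Day 30 | Optional; consent-withdrawal paragraph only |

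The visit is the only item tied to new therapy. The collection and analysis windows run past it for anyone who switches early.

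**2. Days left without a scheduled contact**

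If the visit takes place on day d after the last dose, the uncovered part is 30 − d days. The documents give no distribution of d, so these values are illustrations:

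- d = 10: 20 of 30 days (67%)
- d = 14: 16 of 30 days (53%)
- d = 25: 5 of 30 days (17%)

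**3. Scale for deaths, as a bounded assumption**

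Section 2.1 gives phase 3 deaths (venetoclax versus placebo) as 40 versus 11 in all, 13 versus 1 treatment-emergent, and 27 versus 10 later. The counts add up: 13 + 27 = 40 and 1 + 10 = 11. Safety-set denominators are not stated, but 193 and 96 (inferred) reproduce the printed percentages: 40/193 = 20.7%, 11/96 = 11.5%; 13/193 = 6.7%, 1/96 = 1.0%; 27/193 = 14.0%, 10/96 = 10.4%.

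Suppose the venetoclax rate applied to the roughly 60 subjects here. That is an assumption, because the phase 3 trial used a different combination. Expected treatment-emergent deaths = 60 × 13/193 = 4.04.

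Let f be the share of these that fall after the last dose, and g the share of those subjects whose safety visit had already been brought forward. Neither is given. Expected deaths inside the window but after the last scheduled visit = 4.04 × f × g:

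- f = 0 or g = 0: 0
- f = g = 0.25: 0.25
- f = g = 0.5: 1.0
- f = g = 0.75: 2.3

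These are deaths with no scheduled contact behind them. They are not deaths certain to be missed, since reporting duties still apply.

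**4. Section 5.6 against Appendix D**

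Section 5.6 refers sites to the regular visits. Apart from End-of-Treatment and the safety visit, the regular visits in Appendix D are cycle days, defined by dosing cycles. Appendix E adds that serum and urine electrophoresis continue until progression or withdrawal of consent, which favours continued assessment off drug, but no visit is set for it. SAP Table 1 depends on which visits count as scheduled: progression or death after two or more missing assessments is censored at the last adequate one (or at first dose if there is none). If cycle visits are held to continue off drug and are not done, a later event is censored. If they are not held to be scheduled, there is no missed visit to count.

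**The case against.** Footnote b times a visit; it does not end collection. Section 6.1 keeps the duty to collect to day 30, prompted or not, requires events to be followed until resolved, back to baseline or stable, and requires on-study deaths to be recorded. Section 6.3 adds 24-hour reporting of serious events, and Section 5.4 has medication recorded to 30 days after the last dose. There is an End-of-Treatment visit, and women of childbearing potential with irregular cycles have pregnancy tests 14 and 28 days after the last pomalidomide dose. A Safety Review Committee looks across the venetoclax myeloma studies. All of this stands, and a reader who inferred that events after an early visit fall outside collection would be wrong. What remains is that these duties work only once the site learns of an event, and none gives every early switcher a contact near day 30.

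A reader might also infer from Section 2.1 that the phase 3 excess in deaths lies in the stretch left uncovered. The text does not support that. It places the imbalance mainly in a category that pools deaths during treatment, which this schedule would see, with deaths in the 30 days after it. For deaths beyond 30 days the difference is 14.0% − 10.4% = 3.6 points (95% CI −4.3 to 11.4, inferred denominators), compatible with none. Late deaths were 27/40 (68%) of all deaths on venetoclax but 10/11 (91%) on placebo.

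Finally, the lack of survival follow-up might be read as an error. Overall survival is not an endpoint, the visits were removed deliberately, and late deaths in an uncontrolled study are hard to attribute once other therapy has begun. That is a design choice.

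**Conclusion.** The point holds as a mismatch between the visit schedule and the window that the protocol collects and the SAP analyses. For subjects who switch before day 30, the last part of the window has no guaranteed contact, and in-window events risk selective under-ascertainment although they remain reportable. The number of such subjects is not given. On the assumed phase 3 death rate, deaths falling in the uncovered stretch range from none to about 2 in 60 subjects with f and g up to 0.75, and the lower end cannot be excluded. The conclusion does not rest on those figures; it follows from the text alone.

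Section 5.6 and Appendix D also need to be reconciled, because the documents do not settle what continues after drug is stopped while the SAP counts off-treatment progression in PFS.

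This is a modest, inexpensive improvement to the primary safety data. It is not evidence that the trial will miss a known excess of deaths.

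**What to change.** 1. **Footnote b.** Keep the visit before new therapy. Add a phone contact at about 30 days after the last dose, covering adverse events and vital status, for every subject whose visit was brought forward. Record the start date of the new therapy so that later events can be read against it; the medication record already runs to 30 days after the last dose, so this mainly needs to be made explicit.
2. **Section 5.6 and Appendix D.** Name the contacts and disease assessments, if any, that continue after study drug is stopped for reasons other than progression, and state which of them count as scheduled assessments for the SAP's censoring rules.

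The cost is one call per affected subject and a wording change in two places. Some late-window events will be confounded by the next therapy; the recorded start date allows them to be shown separately but does not remove the confounding. No treatment or eligibility rule changes.
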